Preliminary analyses assume there are no carryover effects. However, sensitivity to this assumption will be examined by considering models that instead assume there are carryover effects (as described above); if there are carryover effects, then the effect of the condition also depends on the period (in addition to possibly gender and NAS-smoking status). For the main analyses that assume there are no carryover effects, we will use uninformative priors for all model parameters. Markov Chain Monte Carlo (MCMC) sampling will be used to estimate the posterior distribution of the model parameters; if there is a convergence issue for a parameter (e.g. if variance hyperparameters are on the boundary) or if model fit is a concern, we will instead consider weakly informative priors.⁵¹ When uninformative priors are used, results using a single candidate model with a Bayesian model averaging approach are equivalent to non-Bayesian, frequentist analyses (i.e. maximum likelihood estimation techniques).

To assess sensitivity of our choice of prior for the carryover effect, we will use a process similar to Grieve (1985).⁴⁸ To allow for a carryover effect, we will first use a Normal distribution with mean 0 and variance σ_{co}^2 as the prior for the carryover effects, and use an uninformative prior for σ_{co}^2 that ranges between 0 and ∞ . Next, we will let π be the prior odds of M_0 to M_1 , where M_0 is the model above without carryover effect and M_1 is the model with carryover

effect. We can then assess the impact of a range of prior belief in a carryover effect by repeating analyses for different values of π . The primary analyses assume there is no carryover effect, which corresponds to π equal to 1, while sensitivity analyses will assume there is a carryover effect, which corresponds to $0 \leq \pi < 1$.

Since MCMC methods will be used, the entire posterior distribution corresponding to the parameters of interest will be estimated and can be produced as figures. Figures may be overlaid to show how results are sensitive to our choice of π . Even though we will obtain the entire posterior distribution of our parameters, we will also calculate 95% credible intervals, which is an alternative way of presenting effect sizes corresponding to hypotheses H(1.1) – H(3.4). Credible intervals will also be used to conduct hypothesis testing (details on hypothesis testing are below). Below are the model outcomes that will be used to test each hypothesis:

H(1.1), H(2.1), H(3.1): Expectancies (Have fewer chemicals)

We will create a binary variable from a 5-point Likert scale (Definitely true, Somewhat true, Neither true nor false, Probably false, Definitely false) for this measurement to indicate if the participant believes the cigarettes smoked during the visit have fewer chemicals (if answered Definitely true or Somewhat true) or not (if answered Neither true nor false, Probably false, or Definitely false). We will use an approach that models the probability of belief that cigarettes smoked during the visit have fewer chemicals, and we will use the logit link function so that the form of the best model will resemble a mixed effects logistic regression model; other link functions (e.g. probit) will be considered if model fit is a concern.

H(1.2), H(2.2), H(3.2): Subjective effects (chemical aftertaste)

Chemical aftertaste will be used as the outcome, which will have items rated on a 100 mm visual analog scale with item-specific anchors (e.g., strength: 0 = "strong chemical aftertaste," 100 = "no chemical aftertaste"). We do not anticipate many measurements on the boundaries (0 or 100), which makes Normality an appropriate assumption for the residuals. However, if there are many measurements on the boundaries (i.e. if Normality does not seem like an appropriate assumption for the residuals), then a binary outcome that indicates if the measurement is greater than 50 will be used instead, and we will use the logit link function so that the form of the best model will resemble a mixed effects logistic regression model (like above for the expectancies outcome); other link functions (e.g. probit) will be considered if model fit is a concern.

H(1.3), H(2.3), H(3.3): Topography (total puff volume)

Normality is expected to be an appropriate assumption for total puff volume (a quantitative variable) based on pilot data.³² However, if Normality does not seem like an appropriate assumption for the residuals in this sample, then a transformed outcome (e.g. log-transformation) will be considered (particularly if the outcome is skewed). If normality is still violated, we will consider a binary outcome using a median cutoff and use the logit link function so that the form of the best model will resemble a mixed effects logistic regression model (like above for the expectancies outcome); other link functions (e.g. probit) will be considered if model fit is a concern.

H(1.4), H(2.4), H(3.4): Biomarkers of exposure (Salivary aldehydes)

Concentrations of formaldehyde and acetaldehyde will be used as the outcome (difference between pre- and post-visit), where Normality is expected to be an appropriate assumption for the error term. However, just as with the other outcomes, if Normality does not

seem like an appropriate assumption, a transformed outcome (e.g. log-transformation) will first be explored, and if normality still does not hold, then we will consider a binary outcome using a median cutoff and use the logit link function so that the form of the best model will resemble a mixed effects logistic regression model (like above for the expectancies outcome); other link functions (e.g. probit) will be considered if model fit is a concern.

Hypothesis testing

H(1.1 - 1.4) are primary, and under the null hypotheses in H(1.1 - 1.4), the natural and organic condition means are equal to the conventional condition means. To test the hypotheses in Aim 1, we will first determine if the effects of the condition depend on gender and NAS-smoking status (as hypothesized in H(2.1) - H(3.4)). If the effect of the condition does not depend on gender or NAS-smoking status, then we will estimate the following effects in our model:

1. effect of the conventional condition
2. effect of the natural condition
3. effect of the organic condition

The null hypotheses in H(1.1 - 1.4) state that the conventional condition is equivalent to the natural and organic conditions. We can therefore test H(1.1 - 1.4) by estimating 95% credible intervals for the difference between the effects of the organic and natural conditions and the conventional condition. This will yield two credible intervals (one for the difference between natural and conventional effects, and another for the difference between organic and conventional effects) for each outcome (four outcomes) therefore making 8 total credible intervals of interest in Aim 1. If the effects of the condition depend on NAS-smoking status but do not depend on gender, then we will estimate the following effects in our model:

1. effect of the own brand condition for Non-NAS smokers
2. effect of the conventional condition for Non-NAS smokers
3. effect of the natural condition for Non-NAS smokers
4. effect of the organic condition for Non-NAS smokers
5. effect of the own brand condition for NAS smokers
6. effect of the conventional condition for NAS smokers
7. effect of the natural condition for NAS smokers
8. effect of the organic condition for NAS smokers

The effect of the condition will then be tested separately by NAS-status. That is, we will calculate 95% credible intervals for the differences between the conventional condition and the natural and organic conditions (organic - conventional and natural - conventional) separately for non-NAS smokers and NAS smokers. This will yield four credible intervals (organic - conventional for NAS smokers, organic - conventional for non-NAS smokers, natural - conventional for NAS smokers, and natural - conventional for non-NAS smokers) for each outcome (four outcomes) therefore making 16 total credible intervals of interest in Aim 1.

If the effects of the condition depend on gender but not NAS-smoking status, then we will estimate the following effects in our model:

1. effect of the own brand condition for men
2. effect of the conventional condition for men
3. effect of the natural condition for men

4. effect of the organic condition for men
5. effect of the own brand condition for women
6. effect of the conventional condition for women
7. effect of the natural condition for women
8. effect of the organic condition for women

The effect of the condition will then be tested separately by gender. That is, we will calculate 95% credible intervals for the differences between the conventional condition and the natural and organic conditions (organic - conventional and natural - conventional) separately for men and women. This will yield four credible intervals (organic - conventional men, organic - conventional women, natural - conventional men, and natural - conventional women) for each outcome (four outcomes) therefore making 16 total credible intervals of interest in Aim 1.

Lastly, if the effects of the condition depend on both gender and NAS-smoking status (as hypothesized), then we will estimate 95% credible intervals for the differences between the conventional condition and the natural and organic conditions separately for non-NAS men, non-NAS women, NAS men, and NAS women. This will yield eight credible intervals for each outcome, so that there are 32 credible intervals of interest (four outcomes each with eight credible intervals) in Aim 1. If it is determined that the natural and organic condition effects can be combined into a single effect (e.g. if the Bayes factor provides evidence for the model that combines the effect over the model that includes separate effects for the natural and organic conditions), then only a single comparison will be made (rather than two comparisons) for the organic/natural conditions in above.

The multilevel modeling approach of Gelman et al. (2012)⁵² will be used to account for multiple comparisons within each aim. The number of comparisons (or contrasts of interest) in Aim 1 (which are based on the following contrasts: organic - conventional and natural - conventional) are determined according to whether the effect of the condition depends on NAS-smoking status or gender, and whether the effects for the natural and organic conditions can be combined (as outlined above). It is relatively straightforward to account for multiplicity within each outcome following the multilevel modeling approach outlined in Gelman et al. (2012).⁵² However, incorporating this approach across the four different outcomes in each aim may not be as trivial; the approach of Westfall (1997)⁵³ may instead be used to account for multiple outcomes.

To test H(2.1) and H(2.2), we will estimate effects for the following subgroups:

1. effect of NAS smokers under the own brand condition
2. effect of NAS smokers under the conventional condition
3. effect of NAS smokers under the natural condition
4. effect of NAS smokers under the organic condition
5. effect of non-NAS smokers under the own brand condition
6. effect non-NAS smokers under the conventional condition
7. effect non-NAS smokers under the natural condition
8. effect of non-NAS smokers under the organic condition

95% credible intervals will be estimated for the difference in effects between 1) 4. - 2. and 8. - 6., 2) 3. - 2. and 7. - 6, 3) 4. - 1. and 8. - 5., and 4) 3. - 1. and 7. - 5. If the credible interval in 1) does not contain 0, then there is evidence (against the null hypothesis) that NAS and non-NAS smokers differ in their mean organic condition outcomes relative to their conventional condition outcomes (otherwise there is evidence for the null hypothesis and therefore no

difference in these two groups). If 2) does not contain 0, then there is evidence (against the null hypothesis) that NAS and non-NAS smokers differ in their mean natural condition outcomes relative to the conventional condition outcomes (otherwise there is evidence for the hull hypothesis and therefore no difference in these two groups). If 3) does not contain 0, then there is evidence (against the null hypothesis) that NAS smokers and non-NAS smokers differ in their mean organic condition outcomes relative to their own brand condition outcomes (otherwise there is evidence for the hull hypothesis and therefore no difference in these two groups). If 4) does not contain 0, then there is evidence (against the null hypothesis) that NAS smokers and non-NAS smokers differ in their mean natural condition outcomes relative to their own brand condition outcomes (otherwise there is evidence for the hull hypothesis and therefore no difference in these two groups). H(2.1) and H(2.2) hypothesizes that there will be evidence against the null hypothesis in 1) and 2) but evidence for the null hypothesis in 3) and 4).

To test H(2.3) and H(2.4), we will estimate the 95% credible intervals corresponding to the difference in means between 6) 4. and 2. above, 7) 3. and 2, 8) 4. and 1., and 9) 3. and 1. If the credible interval in 6) / 7) / 8) / 9) does not contain 0, then there is evidence that NAS smokers mean outcome under the organic / natural / organic / natural condition is significantly different than NAS smokers mean outcome under the conventional / conventional / own brand / own brand condition (evidence against null), otherwise there is evidence that NAS smokers mean outcome is no different in the organic / natural / organic / natural condition compared to the convention / conventional / own brand / own brand condition (evidence for null). We hypothesize that the organic and natural conditions will differ from the conventional condition (i.e. evidence against null in 6) and 7)) but not the own brand condition (i.e. evidence for null in 7) and 8)).

To test H(3.1)-H(3.4), we will estimate effects for the following subgroups:

1. effect of men smokers under the own brand condition
2. effect of men smokers under the conventional condition
3. effect of men smokers under the natural condition
4. effect of men smokers under the organic condition
5. effect of women smokers under the own brand condition
6. effect of women smokers under the conventional condition
7. effect of women smokers under the natural condition
8. effect of women smokers under the organic condition

95% credible intervals will be estimated for the difference in effects between 9) 4. - 2. and 8. - 6., 10) 3. - 2. and 7. - 6., 11) 4. - 1. - (2. - 1.) and 8. - 5. - (6. - 5.), and 12) 3. - 1. - (2. - 1.) and 7. - 5. - (6. - 5.). If the credible interval in 9) / 10) does not contain 0, then there is evidence that men smokers mean outcome under the organic / natural condition relative to the convention condition differs from the women smokers mean outcome under the organic / natural condition relative to the convention condition, which would provide evidence against the null hypothesis in H(3.1) and H(3.2). If the credible interval in 11) / 12) does not contain 0, then there is evidence that men smokers mean outcome difference between the organic / natural condition relative to the own brand condition and convention condition relative to own brand condition differs from the women smokers mean outcome difference between the organic / natural condition relative to the own brand condition and convention condition relative to own brand condition, which would provide evidence against the null hypothesis in H(3.3) and H(3.4) (assuming the direction of the difference is not opposite the hypothesized direction).

Biomarker analyses

Previous work, including our preliminary biosample analyses, demonstrate that short exposures similar to our 15 min ad lib bout increase exposure biomarkers like saliva nicotine (>200-fold) and aldehydes (2-10-fold).^{54,55} Participants' saliva samples (before and after tobacco use sessions) will be characterized for nicotine and aldehyde concentrations and compared across descriptor conditions.

Salivary aldehyde (e.g., acetaldehyde, and formaldehyde) concentrations will be analyzed using O-(2,3,4,5,6-Pentafluorobenzyl)-hydroxylamine (PFBHA, Supelco, Bellefonte, PA) derivatization method. We focus formaldehyde and acetaldehyde as they may make the greatest contribution to cancer risk of all major harmful constituents in mainstream cigarette smoke and because we have demonstrated feasibility of this collection technique to characterize aldehydes in saliva after a 15 min smoking session in our pilot study.³¹ In brief, 1 ml of saliva samples will be added into a 10 ml glass tube. 500 μ l of HPLC grade water, 50 μ l of deuterated internal standard mixture, and 100 μ l of PFBHA solution (250 mg/ml in HPLC grade water) will be added into the glass tube, pH will be adjusted to 3.9 using sulfuric acid, and the sample will be incubated for an hour under room temperature in the dark, and then 200 μ l of sulfuric acid will be added to stop the reaction. 1 ml of dichloromethane (DCM) will be added into the glass tube and shaken well for 1 minute, then the DCM part will be transferred into a new glass tube. This procedure will be repeated three times to ensure all target analytes are extracted. 100 mg of sodium sulfate will be added into the DCM extract and shaken well to remove remaining water. The DCM fraction will be transferred to toluene (final volume=200 μ l) under gentle stream of nitrogen. The sample will be injected into gas chromatography (GC)-mass spectrometer (MS) for aldehyde-PFBHA quantification (PerkinElmer Clarus 680 GC and Clarus SQ 8T MS, PerkinElmer, Waltham, MA). Injection volume and injector temperature will be 1 μ l and 250 °C, respectively. The target analytes will be separated using PerkinElmer Elite-5MS column (L=30 m, ID=0.25 μ m, DF=0.25 μ m) with column oven gradients starting at 40 °C, hold for 2 minutes, increase to 230 °C at 5 °C/minute gradient, hold for 2 minutes, then increase to 325 °C at 20 °C/minute gradient, and hold for 5 minutes. Limit of detection (LOD) and limit of quantification (LOQ) for formaldehyde-PFBHA are 0.34 ng/ml and 1.13 ng/ml, respectively, and acetaldehyde-PFBHA are 0.41 ng/ml and 1.37 ng/ml, respectively.

To measure nicotine (NIC), cotinine (COT), and trans-3'-hydroxycotinine (3OHC), 200 μ l of saliva will be transferred into a micro-centrifuge tube. Known amounts of deuterated internal standards (NICd3, COTd3, and 3OHCd3, Cayman chemical, Ann Arbor, MI) will be added into the tube as an internal standard. The tube will be stored for 10 minutes in 4 °C refrigerator after adding 750 μ l of glacial acetone, followed by centrifuging at 3000 g for 30 minutes. The supernatants will be collected in a new micro-centrifuge tube, 150 μ l of methanol will be added into the tube and concentrated until 100 μ l under gentle stream of nitrogen. The sample will then be transferred into an amber autosampler vial and 10 μ l of the sample will be injected into an Ultra Performance Liquid Chromatography (UPLC)-tandem mass spectrometer (MS/MS) (Waters Aquity UPLC and Xeto TQ-S MS/MS, Waters, MA, USA) equipped with a Waters BEH C18 column (1.7 μ m, 2.1×50 mm, Waters, MA, USA). The column will be heated at 35 °C. Methanol with 0.1% Formic acid and HPLC-grade water with 0.1% Formic acid will be used as phase A and B. Mobile phase gradient (0.3 ml/minute) will be 21% phase A at 0 minute and hold for 0.8 minutes, increase to 90% phase A in 0.4 minutes and hold for 0.9 minutes, then decrease to 21% phase A in 0.2 minutes and hold for 0.7 minutes. Target analytes will be identified using 25 V cone voltage and 35 V collision voltage. Parent and daughter m/z are 163 and 132 for NIC (166 and 132 for NICd3), respectively, 177 and 80 for COT (180 and 80 for COTd3), respectively, and

193 and 80 for 3OHC (196 and 80 for 3OHCd3), respectively. LOD for NIC, COT, and 3OHC are 1.20 ng/ml, 5.70 ng/ml, and 6.22 ng/ml, respectively, and LOQ for the compounds are 4.01 ng/ml, 19.0 ng/ml, and 20.7 ng/ml, respectively.

REFERENCES

1. U.S. organic sales break through \$50 billion mark in 2018 17 May 2019, 2019. Accessed 13 July 2020. <https://ota.com/news/press-releases/20699>
2. Lee W-cJ, Shimizu M, Kniffin KM, Wansink B. You taste what you see: Do organic labels bias taste perceptions? *Food Qual Prefer.* 2013;29(1):33-39. doi:10.1016/j.foodqual.2013.01.010

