The overall purpose of this study is to examine the relationship between the “organic” and “natural” descriptors and health risk expectancies, subjective effects, topography, and resulting chemical exposures. This is a within-person human laboratory study with assessments of psychological, behavioral, and biological exposure data. The procedures described here were tested in a pilot study conducted in late 2019.³² Data will be collected at the University of Nevada, Reno (Reno, Nevada, USA), the Desert Research Institute (Reno, Nevada, USA), and the University of Pennsylvania (Philadelphia, Pennsylvania, USA). The study will consist of 5 total lab visits: the baseline visit, and four experimental visits (own brand comparator condition, “natural” advertising condition, “organic” advertising condition, and “conventional” advertising condition) (Figure 1). Conditions will be randomized and counterbalanced to account for order effects.

This is a deception study; participants will believe that they are participating in market testing cigarettes and will not know the real purpose of the study. We created a faux tobacco brand and associated cigarette mailer for the organic, natural, and conventional cigarette varieties (Figure 2). While participants will believe they are testing three varieties of a new brand of cigarette, in reality they will use the same product (Nat’s “Rich Smooth Taste” cigarettes, the blinded experimental cigarette) three times. None of the labs involved in data collection are in medical or public health-focused buildings, which aids in the study deception. Results from our pilot study demonstrate that this study design will deceive participants.³² At the last pilot study visit, we asked our 22 pilot study participants to restate the purpose of the study as they saw it. Though a handful of participants inferred that things weren’t *exactly* as they seemed, none of the participants described the actual study purpose. We will include the same question at the end of Session 5 to identify participants who were not deceived by the study (see Missing Data).

Aims & Hypotheses

Aim 1 hypotheses are primary; Aims 2 and 3 hypotheses are secondary. The specific aims and associated hypotheses are:

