Session 2 is the participant’s own brand assessment. Study personnel will collect a CO reading (to confirm abstinence), assess harm perceptions pre-administration of the product, collect a saliva sample, allow the participant to smoke their cigarettes (ad lib) for 15 minutes (consuming as much as they like) with the topography equipment attached, assess subjective effects, collect a saliva sample and CO reading directly after self-administration, and administer the purchase task. The purpose of this session is to understand how reinforcing participants find their own brand and is useful for disentangling the effect of the exposure from the effect of smoking a novel cigarette. For example, if topography results are null, we can use the OB condition topography data to evaluate to what degree are our results due to participants not liking the experimental cigarette. We will also use data from Session 2 to describe NAS smokers’ OB evaluations and to compare them to non-NAS smokers’ OB evaluations. Collecting expectancies and subjective effects will help us understand the motivations NAS smokers have for using their preferred brand.

Sessions 3-5 are the experimental exposure sessions and will have identical protocols other than the introduction of different advertising exposures. Study personnel will collect a CO reading (to confirm abstinence) and a saliva sample, introduce the cigarette to be used that day (see “Description of the exposure”), assess participants’ expectancies, measure their smoking topography for 15 minutes of ad lib use, collect their subjective impressions of the cigarette, and

collect a second CO reading and saliva sample. During the final session, we will debrief the participant about the study (including clarification that “organic” and “natural” cigarettes are not reduced-harm products) and assess whether participants were deceived by the protocol by asking them to re-state their understanding of the purpose of the study.

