We will consider models that: 1) allow the effect of the condition (conventional, organic, and natural) to differ based on NAS-smoking status and gender (as hypothesized); 2) allow the effect of the condition to differ based only on NAS-smoking status; 3) allow the effect of the condition to differ based only on gender; and 4) do not allow the effect of the condition to differ based on NAS-smoking status or gender. We will also consider models that combine the effects of the natural and organic conditions, as we believe the effects of these two conditions could be similar for our outcomes. We will also consider in the model an effect for the own brand

condition (which may or not depend on NAS-smoking status and gender), period effects, random effects, and effects for other covariates that may be predictive of the outcome. Bayes factors will be used to determine if the effect of the condition depends on NAS-smoking status or gender, and if a combined effect (one effect vs two) should be used in the model for the natural and organic conditions.

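### Own brand is always smoked in the first smoking session, so the within-NAS own-brand contrasts for H2.3 and H2.4 cannot separate a brand effect from a first-session effect

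*Combined protocol and SAP*

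**What the plan says.** All places are in the combined protocol and SAP.

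- **Study overview.** After a baseline visit there are four experimental visits: own brand (called a comparator), natural, organic and conventional. Two sentences later comes "Conditions will be randomized and counterbalanced to account for order effects".
- **Study procedures.** "Session 2 is the participant’s own brand assessment". Then: "Sessions 3-5 are the experimental exposure sessions and will have identical protocols other than the introduction of different advertising exposures". The order of own brand is thus the same for every participant.
- **Statistical analyses, candidate models.** "We will also consider in the model an effect for the own brand", continuing "condition (which may or not depend on NAS-smoking status and gender), period effects, random effects, and effects for other covariates". The coding of period is not given. The main analysis uses uninformative priors for all parameters.
- **Hypothesis testing, H(2.3) and H(2.4).** Within NAS smokers, contrasts 6) and 7) compare organic and natural with conventional. The own-brand comparisons are "8) 4. and 1., and 9) 3. and 1", that is, organic minus own brand and natural minus own brand. An interval that contains 0 is to be taken as evidence of no difference, and no difference from own brand is the stated expectation. (The closing sentence there labels the own-brand pair 7) and 8); from the definitions it must mean 8) and 9).)
- **Aims & Hypotheses.** H2.3 and H2.4 themselves say only that conventional will be lower than natural, organic and own brand. The expectation of no difference from own brand appears only under Hypothesis testing.

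**The concern.** If own brand were rotated through Sessions 2-5, as the Study overview can be read to say, a period effect would be balanced over the four conditions. With own brand always first, anything particular to the first smoking session goes into the own-brand mean, for instance the first bout after required abstinence or the first recorded ad lib bout with the topography device attached.

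Contrasts 8) and 9) are taken within one group, so nothing cancels. A session effect could produce a difference from own brand that has nothing to do with brand. An effect in the other direction could mask a real difference, and the plan would then report that as support for its expectation. The planned sensitivity analysis deals with carryover. It does not deal with a main effect of period.

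**Working it through.** **1. The plan's own figure, to check the SD and correlation used below.** Inputs from Sample size calculations: mean difference 120 ml, SD 165 ml, correlation 0.5, 5% level (two-sided assumed), 90% power, effect halved, covariance 50% larger.

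- SD of a within-person difference = 165 × √1.5 × √(2 × (1 − 0.5)) = 202.1 ml
- n = ((1.96 + 1.2816) × 202.1 / 60)² ≈ 119.2, so 120

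This matches the plan's 120 subjects (122 with the noncentral t). With the covariance not inflated, the SD of a difference is 165 × √(2 × 0.5) = 165 ml.

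**2. Rank check.** Take the six orders of the three descriptor conditions over Sessions 3-5, with own brand always at Session 2. One subject per order gives 6 subject columns, 3 condition columns (natural, organic, own brand; conventional as reference) and 3 period columns (Sessions 3, 4, 5; Session 2 as reference), 12 in all. The own-brand column equals the sum of the subject columns minus the sum of the period columns, which is the Session 2 indicator.

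| Layout | Columns | Rank | Natural or organic minus conventional | Natural or organic minus own brand |
|---|---|---|---|---|
| Own brand at Session 2, free periods | 12 | 11 | estimable | not estimable |
| Own brand at Session 2, linear period | 10 | 10 | estimable, variance 2σ²/n | estimable only by extrapolating the trend, variance 4σ²/n |
| Own brand at Session 2, periods for Sessions 3-5 only | 11 | 11 | estimable | estimable as brand plus first session |
| Own brand rotated, 24 orders, free periods | 30 | 30 | estimable | estimable, variance 2σ²/n |

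**3. Two groups.** With NAS and non-NAS groups, group-specific condition effects and common free periods, the rank is 20 of 21. The within-NAS own-brand contrasts are not estimable. The NAS minus non-NAS difference in organic minus own brand is estimable, because the common period effect cancels. It is lost again if period effects differ between groups.

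**4. Which tests are touched.**

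- Aim 1 contrasts, and 6) and 7): both arms of each contrast lie in Sessions 3-5. Not affected.
- H3.3 and H3.4: organic minus own brand, less conventional minus own brand, is (4 − 1) − (2 − 1) = 4 − 2. Own brand drops out. Not affected.
- Contrasts 3) and 4) for H2.1 and H2.2: protected if period effects are common to both groups.
- Contrasts 8) and 9): affected.
- Conventional against own brand (2. against 1.), which H2.3 and H2.4 state: never listed under Hypothesis testing, and aliased in the same way if added.

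**5. Illustration of size, with period left out.** Assumptions: 114 NAS completers (half of the 228 targeted), brand has no effect, and a pure first-session shift d, for which the documents give no value. SE = 165/√114 = 15.5 ml to 202.1/√114 = 18.9 ml. The probability that the 95% interval excludes 0 is Φ(d/SE − 1.96) + Φ(−d/SE − 1.96).

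| Shift d | SE 18.9 ml | SE 15.5 ml |
|---|---|---|
| 20 ml | 18% | 25% |
| 40 ml | 56% | 74% |
| 60 ml | 89% | 97% |

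A shift of 1.96 SE, or 30-37 ml, excludes 0 half of the time.

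**The case against.** **The Study overview may mean only the descriptor conditions.** It calls own brand a comparator, Statistical analyses lists condition as organic, natural or conventional, and Figure 1 is not available here. This is fair, and on that reading the sentence only needs clarifying. The confounding remains, because Study procedures fixes Session 2.

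**There is a reason to collect own brand first, and there are safeguards.** Own-brand data are meant to separate the exposure from the effect of a novel cigarette, and own-brand puff volume is listed as a baseline covariate. Session 1 familiarises participants with the topography device. Every smoking session requires 12 hours of abstinence, a CO check and a similar time of day. These measures make a first-session effect smaller but do not exclude it, and the data cannot show that it is absent.

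**The plan only considers period effects and gives no coding.** This stands. Exact aliasing needs free period effects that include Session 2. Omitting period or making it linear removes the rank deficiency, but the own-brand contrast then rests on an assumption that the design cannot test. Non-identification and the bias illustrated above are alternatives: the first arises if free periods are fitted, the second if period is omitted.

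**Stronger readings.** A reader might infer that the whole model, and with it the primary analysis, is unidentified. The rank check shows otherwise. A reader might also infer that a shift of 30-37 ml is sure to overturn the result, or that such a shift is expected. At that size exclusion of 0 is an even chance, and no document gives any shift.

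**Conclusion.** The point holds for contrasts 8) and 9) of H2.3 and H2.4, which are secondary. As designed, these estimate a combined brand-and-first-session difference. Neither an interval that excludes 0 nor one that contains it can be attributed to brand alone, so the plan's reading of the latter as support for the null is not justified.

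The fixed order and the algebra come straight from the documents. The size does not: the 18-97% range depends on an assumed shift of 20-60 ml, on 114 completers, on period being omitted and on a normal 95% interval without the planned multiplicity modelling. It covers puff volume only; the documents give no SD for aldehydes, so H2.4 is not quantified.

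**What to change.** 1. In the Study overview, say that only the three descriptor conditions are randomised and counterbalanced, over Sessions 3-5. Reconcile the sentence in Study procedures that has participants smoking the experimental cigarette in Sessions 2-5 with the own-brand session.
2. In Statistical analyses, fit period effects for Sessions 3-5 only and state the coding. With effects that sum to zero, the own-brand difference is taken against the average over Sessions 3-5; with a reference session, it is taken against that session.
3. Under Hypothesis testing, report 8) and 9) as descriptive brand-and-first-session differences and remove the reading of an interval containing 0 as support for the null. Treat conventional against own brand in the same way if it is added, and correct the 7) and 8) label.
4. Contrasts 3) and 4) may be shown alongside, with the common-period assumption stated. They should not replace 8) and 9): they ask whether NAS and non-NAS smokers differ, and could be zero while NAS smokers differ greatly from own brand. They are also less precise (202.1 × √(2/114) = 26.8 ml against 18.9 ml).

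No visit changes. The cost is a weaker secondary claim: the own-brand part of H2.3 and H2.4 is no longer confirmatory. Rotating own brand over Sessions 2-5 would keep it confirmatory, but that changes the design.
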